## SUMMARY TABLE

Title	A Pilot Study of FDA Approved Optiflow™ THRIVE versus Standard Non-Rebreathers in Patients with Potential High Risk of Airway Obstruction during Total Intravenous Anesthesia Procedures
Project Office	Division of Anesthesiology, Critical care and Pain Management; FC13.2036
Study Size (# of patients)	A proposed sample size of eligible 120 patients (60 patients randomized equally between two groups)
Study Design	This is a prospective randomized trial. All the eligible subjects will be randomly assigned to one of two groups: the Optiflow THRIVE group or the standard non-rebreather group.
Primary Objective	To investigate the performance of Optiflow™ THRIVE relative to Standard Non-Rebreathers in patients with high risk of difficult airway management undergoing total intravenous anesthesia (TIVA) procedures.
Secondary Objective(s)	To describe the episodes of hypoxia (defined by $\text{SpO}_2 \leq 92\%$ ) and the episodes of airway support which include: jaw thrust, chin lift or insertion of an airway supporting device, such as oral/nasal airway or supra airway device in order to recover the level of oxygenation above 92% associated with Optiflow™ THRIVE.
Inclusion Criteria	A patient who meets all the following criteria may be included in the study: 1. 18 years of age and older and signed consent for the study 2. Presents with a $\text{SpO}_2 \geq 95\%$ while breathing room air 3. Requires TIVA but not tracheal intubation during the proposed procedure – PLUS, any of the following: Body mass index (BMI) $\geq 32 \text{ kg/m}^2$ ; neck circumference $\geq 43 \text{ cm}$ in a male and $41 \text{ cm}$ in a female patient; has been diagnosed with moderate to severe obstructive sleep apnea (OSA) by a sleeping study with/without using a continuous airway pressure (CPAP) device; or, full course head and neck radiotherapy $\leq 6$ months (The peak onset time of acute facial and airway edema)

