## 1. OBJECTIVES

**Primary:** To investigate the performance of Optiflow™ THRIVE relative to Standard Non-Rebreathers in patients with high risk of difficult airway management undergoing total intravenous anesthesia (TIVA), for the planning of future clinical studies.

**Secondary:** To describe the episodes of hypoxia (defined by  $\text{SpO}_2 \leq 92\%$ ) and the episodes of airway support which include: jaw thrust, chin lift or insertion of an airway supporting device, such as oral/nasal airway or supra airway device in order to recover the level of oxygenation above 92% associated with Optiflow™ THRIVE.

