### 3. STUDY DESIGN DESCRIPTION

This is a prospective randomized controlled study. Patients will be randomized in a 1:1 fashion to one of two study groups, the treatment group or control group. The patients in the treatment group will receive oxygen via Optiflow™ THRIVE; while the patients in the control group will receive 100% oxygen via a non-rebreather facemask. CORe will be used to conduct the randomization, as well as random block sizes; recommending to CORe that block sizes of 2, 4, 6, and 8 are allowable. Blocking will be utilized to maintain exactly 50 patients per study group. Patient randomization will occur after a patient has been deemed eligible and consented to participate. The data below listed will be collected during the procedure and statistically compared between the two groups at the end of the study.

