## 7. METHODS AND STUDY PROCEDURES

Patients will be randomized into 1 of the 2 arms of the study, the intervention group and control group, by the use of randomizing software (CORe) to indicate which study group the patient has been assigned to. The patients in intervention group will be given 100% oxygen via Optiflow THRIVE with a flow rate of 50 L/minute for a period of 3 minutes prior to anesthetic induction and 70 L/minute thereafter anesthetic induction until the end of procedure; and the patients in control group will receive 100 % oxygen at the flow rate of 8 L/minute via a non-rebreather mask for 3 minutes prior to anesthetic induction and maintain the same flow rate until the end of procedure. The type of anesthesia for both groups will be total intravenous anesthesia (TIVA) without a tracheal intubation or super laryngeal airway support. The anesthesia for both groups will be induced with propofol boluses or continuous infusion. The dose of boluses or the infusion rate will be the decision of anesthesiologist. However, midazolam or fentanyl is generally avoided during the study to avoid the synergistic effects in respiratory depression. The quality of anesthesia (the depth and amnesia effect of anesthesia) is monitored by a BIS device with reading between 40-60, as satisfactory. The study coordinator will be responsible to follow the study procedures, to ensure the validity and integrity of the study protocol. The study coordinator will also be responsible for data collection when the 60-minute assessment window for monitoring begins. All data collection will take place prior to, and during, the patient's scheduled IR procedure. The 60-minute assessment window will begin after induction (initial Propofol administration; bolus), once induction has been recorded in the patient's electronic medical record via online time stamping in EPIC, and will conclude 60-minutes after (the recorded time of induction). Total length of desaturation episode(s) (ToLDE) will be recorded by utilizing a stop-watch/clock. All other collected data will be recorded via observation and patient monitoring during the procedure. The following data will be collected during the procedure and statistically compared between two study groups after completion of data collection (see **Appendix A.**):

1. Patient's demographic information
2. Patients underline diagnosis and ASA Physical Status
3. Procedure data, name, duration and position

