4. Episodes and percentage duration of oxygen desaturation defined by  $\text{SpO}_2 \leq 92\%$  over the entire procedure
5. Episodes of manual airway support, including jaw thrust, or insertion of an artificial airway device
6. Episodes and duration of BIS number  $\geq 61$  during the entire procedure
7. Episodes of patient movement during the procedure
8. The total dose of propofol used during the entire procedure
9. Patient satisfaction after the procedure by post PACU discharge evaluation (see **Appendix B.**)

**Preoperative care:** No active intervention is planned on this phase of care. All procedures will be provided according to routine clinical care and clinical judgment.

**Intraoperative care:** Total intravenous anesthesia (TIVA) will be delivered using an intravenous infusion of propofol according to anesthesiologist clinical judgment. Intraoperative hemodynamic and temperature will be monitored and maintained according to routine clinical care. A BIS monitor measures the depth of anesthesia with reading between 40-60, as satisfactory.

**Postoperative care:** All patients will be monitored in PACU according to routine clinical care. If deemed necessary by the attending anesthesiologist, patients will be transferred to the intensive care unit.

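### The primary endpoint is timed by stop-watch/clock, apparently by a coordinator who can see the device; a masked, programmed derivation from stored SpO2, where one exists, could reduce arm-dependent timing error

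*Combined protocol and SAP*

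**What the plan says.** The primary endpoint is total desaturation time, in minutes, over a fixed 60-minute window, with desaturation defined as SpO2 of 92% or less (section 6.1). Section 7 gives the only stated method of measurement: "Total length of desaturation episode(s) (ToLDE) will be recorded by utilizing a stop-watch/clock". On who does it, section 7 says "The study coordinator will also be responsible for data collection when the 60-minute assessment window for monitoring begins". The remaining items are handled similarly: "All other collected data will be recorded via observation and patient monitoring during the procedure". The one electronic time described is that of induction, recorded "via online time stamping in EPIC"; it anchors the window but is not an SpO2 record.

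The two arms look different. Control patients "will receive 100% oxygen via a non-rebreather facemask" (section 3), while the others wear the nasal high-flow device.

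Data item 4 in section 7 is a second desaturation measure, beginning "Episodes and percentage duration of oxygen desaturation defined by". It covers the whole procedure, not the 60-minute window.

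Sections 11.2 and 11.3 provide for source documents and for checking case report forms against them, without naming an SpO2 record among the sources.

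**The concern.** Whoever holds the clock decides when to start, when to stop, and whether a brief dip or a lost signal counts. By section 7, airway support, BIS and patient movement are recorded during the same procedure. The allocated device is in plain view, and the text mentions no masking of the assessor.

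Random timing error of equal size in both arms only widens the interval. Error that differs by arm, such as dips missed or noted late, or clocks stopped early, goes straight into the difference in mean ToLDE. The 95% CI planned in section 6.1 would not reflect it.

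The trial is a pilot, run "for the planning of future clinical studies" (section 1), and section 4.1 says existing data do not support a power analysis. What is at stake is therefore a distorted difference or SD carried into the next design, not a wrong confirmatory test.

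**Working it through.** **The plan's own figure.** Section 6.1 gives a half-width of 0.39 with 50 per group and SD 1.0. The half-width for a difference of two means is 1.96 × 1.0 × √(2/50) = 0.392, which agrees. The SD of 1.0 is a working value, so it says nothing about real timing.

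**Equal random error.** Adding timing error with SD 0.25 to both arms gives 1.96 × √((1 + 0.0625) × 2/50) = 0.404. With SD 0.50 it gives 0.438. The effect is a loss of precision only.

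**Arm-dependent error.** The documents give no episode rate, timing error or observed SD, so these are assumptions:
- a share p = 0.3 of patients desaturate;
- ToLDE among them is exponential with mean m = 1, 2 or 5 min;
- there are n = 50 per arm and no true difference;
- in one arm only, recorded time is too short by e = 10 s or 30 s per affected patient, and cannot fall below zero.

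Step 1, spread: SD = m × √(2p − p²) = m × √0.51, which is 0.714, 1.428 or 3.571 min.

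Step 2, half-width: 1.96 × SD × √(2/50) = 16.8, 33.6 or 84.0 s.

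Step 3, shift in the mean difference: p × m × (1 − exp(−e/m)), with e and m in the same unit. For m = 60 s and e = 30 s this is 0.3 × 60 × (1 − exp(−0.5)) = 7.1 s.

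Step 4, coverage of the 95% t interval, from 40,000 simulated trials per setting:

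| Mean ToLDE if affected | No error | 10 s error: shift, coverage | 30 s error: shift, coverage |
|---|---|---|---|
| 1 min | 95.4% | 2.8 s, 94.2% | 7.1 s, 84.4% |
| 2 min | 95.4% | 2.9 s, 95.1% | 8.0 s, 92.5% |
| 5 min | 95.3% | 3.0 s, 95.3% | 8.6 s, 94.9% |

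If instead 20% of desaturation time is missed in one arm, the shift is 0.2 × 0.3 × m = 3.6, 7.2 or 18 s, and coverage is 93.7% to 93.8% for all three means.

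**Do other passages close the gap?** Item 4 covers a different period and falls under data recorded by observation and monitoring, so it is not shown to be electronic or independent. If the stopwatch entry is itself the source document, checking the form against it cannot reveal a missed dip. The start and end of an episode are implied: the threshold gives the start, and the secondary objective in the Summary Table ("in order to recover the level of oxygenation above 92"%) gives the end. They are not part of this point.

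**The case against.** The strongest reply is that no error has been shown. The observer reads a number against a fixed threshold and does not judge a subjective state, which limits how far knowing the arm can distort the timing. The devices cannot readily be disguised, and stopwatch timing is workable. Of the six fixed-error settings above, only one shows a clearly material loss of coverage, and there the assumed 30 s error is half of the 1-minute mean. All of this stands, and it limits the weight of the point.

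It is also fair to say that rules for minimum duration, artefact and signal loss may sit on the Appendix A forms, which are listed by title only. Their absence from the supplied text cannot be asserted as a gap in the plan.

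Two stronger readings are tempting. A reader might infer that the ToLDE comparison will be biased, or that deriving it from SpO2 data would remove the bias. The documents support neither. They give no size or direction for any error, and a programmed derivation acts only on observer timing, not on signal artefact or on care given with the arm known. A reader might also treat every late or missed reading as a full loss of e seconds. At m = 1 min and e = 30 s that gives a 9 s shift and, by normal approximation, 81.7% coverage. Recorded time cannot go below zero, however, so under-timing gives the smaller effect tabulated.

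What survives is that a specific, more objective method could replace the stated one at little cost, and that nothing in the supplied text already does so.

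**Conclusion.** The point holds as a measurement improvement worth making, not as a demonstrated bias. The primary endpoint rests on manual timing, apparently by someone who can see the allocation, with no masking and no stored SpO2 source in the supplied text. Under the stated assumptions, coverage runs from about 95% (10 s error, or mean ToLDE of 5 minutes) down to about 84% (30 s error, mean of 1 minute, shift of about 7 s). The concern is material only if episodes are short or the arm-dependent error reaches tens of seconds per affected patient. The documents cannot say which case applies, and the supplied text describes nothing in the trial that would show it. Confidence is moderate, because the Appendix A forms are unseen and the existence of a stored trend is unknown.

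**What to change.** In section 7, establish whether the monitor or anesthesia record stores time-stamped SpO2, and state its interval.

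- **If the interval is short relative to the episodes:** make that record the source for ToLDE and for episode counts. Derive both by program, masked to arm, over the 60 minutes from the EPIC induction stamp. Write the minimum-duration and artefact/signal-loss rules in advance. Keep the stopwatch as back-up and report agreement between the two by arm.
- **If only a coarse trend is stored:** keep the stopwatch as the primary source and use the trend as a masked sensitivity check.
- **If nothing is stored:** keep the stopwatch, with the same written rules.

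Use data item 4 as a cross-check only if it is recorded independently and can be limited to the same window.

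The cost is one export per patient, one tested script, the written rules and one agreement table. Sample size and patient procedures do not change. A linkage step is also needed. Section 11.5 says that names and record numbers will not be collected and that the linking code is destroyed after the study, so each export must be matched to the study ID while that link exists. Section 11 describes REDCap's import facility in general terms only; it is not evidence of a working monitor export. The downside is that the gain depends on an adequate stored trend, and resolution is limited by its interval.

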## 8. SUBJECT WITHDRAWALS

Subjects will be advised in the written informed consent forms that they have the right to withdraw from the

study at any time without prejudice. Should a patient withdraw from the study, the study data collection will be terminated. The standard clinical pathway in destroying the confidential patients' health information will be used to handle the collected data.

Subjects may be withdrawn from the study for the following reasons (but not limited to):

1. Subject non-compliance with study procedures
2. Unacceptable adverse events (safety or tolerability)
3. Voluntarily withdraw (at any time, for any reason)
4. Physician discretion

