### 4. DISCUSSION OF SUBJECT POPULATION

#### 4.1 Subject Characteristics

- a) **Total number of subjects:** Due to lack of existing data to support a power analysis, the estimated number of study subjects is currently 120 eligible patients with 60 in each group. Due largely to the variation of caseload daily in IR, the average caseload for the study is expected no more than 2 cases/day. With the safety profiles in the previous reports mentioned above, the failure rate or the subject withdraw from the study is estimated no more than 1%.

All included cases will be scheduled elective procedures. Although we expect the rate of patient withdrawal to be low, we will not replace missing slots in the randomization list with the next eligible patient. Those patients will be considered randomized, but unevaluable. If needed, a protocol amendment will take place to increase the total number of randomized patients, only if this turns out to be an issue.

- b) **Study subjects:** Optiflow™ is a standard airway device used routinely and internationally, for high flow nasal oxygen (HFNO) delivery. Multiple studies have demonstrated that Optiflow™ is superior to the existing comparable devices in terms of both oxygenation and CO2 clearance. In addition, its safety profile in maintaining a patent airway is also superior to comparable devices during deep

sedation or general anesthesia (GA) without tracheal intubation. Standard anesthetic care will be provided to all patients with the exception of whether the patients receive HFNO or oxygen via non-rebreather face mask. Thus far, the literature has not demonstrated use in the pediatric population; patients < 18 years of age will not be included in this trial.

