## 9.3 Responsibilities for Reporting Serious Adverse Events

The PI will record all serious adverse experiences that occur during the study period in the appropriate source documents and/or AE log as applicable.

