## 9.6. Investigator Reports and Responsibilities

Investigators are responsible for ensuring the investigation is conducted in accordance with the study protocol and applicable Federal regulations (21 CFR, Part 812, Subpart E). Investigators are also responsible for:

- Obtaining IRB approval for study conduct and re-approval as applicable (if more than one Investigator is participating in the study at a site, the Principal Investigator shall be responsible for the IRB approval and re-approvals)
- Obtaining informed consent of study subjects prior to enrollment into the clinical study
- Protecting the subject rights, safety, and welfare
- Maintenance of subject records and confidentiality
- Record retention as defined in Federal regulations 21 CFR, Part 812.140 (a), (d), and (e)
- Management of investigation and study related activities according to the Clinical Investigator Agreement and the Study Research Agreement
- Submission of site-specific study closure report to governing IRB within 3 months of notification from study Sponsor (if more than one Investigator is conducting the study, the Primary Investigator is responsible for submission of the study closure report)
- Return of any unused investigational product to the study Sponsor upon request or at the conclusion of the clinical study

In addition:

- An Investigator shall report to the Sponsor, within 5 working days, a withdrawal of approval by the reviewing IRB of the Investigator's part of an investigation
- If an Investigator uses a device without obtaining informed consent, the Investigator shall report such use to the Sponsor and the reviewing IRB within 5 working days after the use occurs
- An Investigator shall, upon request by a reviewing IRB or regulatory agency official, provide accurate, complete, and current information about any aspect of the investigation

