### 10.2 Protection Against Risks (Risk Minimization)

The data collection will be terminated if an identifiable adverse event happens. The event will be handled and reported according the standard clinical pathway.

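### Section 8 sends a withdrawn patient's collected data to a destruction pathway with no exception for adverse-event or physician withdrawals, which permits outcome-related loss of ToLDE data and contradicts the safety-recording and retention sections

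*Combined protocol and SAP*

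**What the plan says.** Section 8 (Subject Withdrawals) has two parts. The first concerns the patient's right to withdraw: "Should a patient withdraw from the study, the study data collection will be terminated". The next sentence deals with data already collected: "The standard clinical pathway in destroying the confidential patients' health information will be used to handle the collected data". The second part lists reasons for which subjects may be withdrawn: non-compliance, "Unacceptable adverse events (safety or tolerability"), voluntary withdrawal and physician discretion. The list carries no data rule of its own.

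Section 4.1 says that slots lost to withdrawal are not refilled, and adds: "Those patients will be considered randomized, but unevaluable". It puts failure or withdrawal at no more than 1%. Sections 6.1 and 6.2 name no intention-to-treat set and give no rule for an incomplete ToLDE.

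Other sections point the opposite way on safety records. Section 9.2 wants every adverse event documented on the Adverse Event Form and UADEs sent to the Sponsor within 24 hours. Section 9.3 states: "The PI will record all serious adverse experiences that occur during the study period". Sections 9.6 and 9.7 bind the investigator and the Sponsor to record retention under 21 CFR 812.140.

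**The concern.** The primary endpoint is minutes at SpO2 of 92% or below in the 60 minutes after induction. Patients are anesthetized in that window, so a withdrawal inside it would in practice be the physician's decision. The documents describe no blinding of the treating team. Severe desaturation can therefore be both a high value of the endpoint and a reason for withdrawal. If the single data rule in section 8 covers such cases, the arm with more failures loses its longest ToLDE values and the group difference is pulled toward zero.

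The pilot's stated purpose (section 1) is to plan later studies, so the spread and upper tail of ToLDE are among its main products. Both would be understated. Section 7 has ToLDE timed by stop-watch or clock, and the documents describe no second source for it, so later analysis may be unable to restore a destroyed value.

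On safety, a site that follows section 8 to the letter could breach sections 9.2, 9.3, 9.6 and 9.7.

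**Working it through.** **1. The plan's own figure.** Section 6.1 gives a half-width of 0.39 with 50 per group, SD 1.0 and a two-sided 95% CI. For a difference in means, 1.96 × 1.0 × √(2/50) = 0.392, which reproduces it. A single-mean interval would give 1.96/√50 = 0.277, so the stated figure is for the between-group difference. With SD 1.0, the 0.39 can be read in SD units.

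**2. Expected number of losses.** At the 1% in section 4.1, 0.01 × 120 = 1.2 patients in total, or 0.6 per arm. The allowance from 60 to 50 is 10/60 = 16.7%, but section 6.1 ties it to interventional radiology procedure changes, not to withdrawals.

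**3. Shift in one arm's mean.** If k of 60 patients, on average m SD above the arm mean, are removed, the mean of the rest falls by k × m/(60 − k) SD. For example, one patient 3 SD above the mean gives 3/59 = 0.051 SD, and five such patients give 15/55 = 0.273 SD.

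**4. Worst-case removal.** The documents give no ToLDE data, so three shapes were assumed. For each, 40,000 samples of 60 standardized values were drawn, the k largest were removed, and the fall in the mean was averaged (in SD):

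| Largest removed, of 60 | Normal | Exponential | Half zeros, rest exponential |
|---|---|---|---|
| 1 | 0.039 | 0.062 | 0.068 |
| 2 | 0.073 | 0.110 | 0.119 |
| 3 | 0.105 | 0.150 | 0.161 |
| 5 | 0.163 | 0.218 | 0.231 |
| 10 | 0.294 | 0.350 | 0.360 |

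Against 0.392, losing the worst one is 10% to 17% of the half-width, the worst five 42% to 59%, and the worst ten 75% to 92%. Under each shape these are the largest expected shifts for that k, because all losses are taken from one arm and from its extreme values.

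**5. The provisions side by side.**

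| Question | Section 8 or 4.1 | Elsewhere |
|---|---|---|
| Data already collected at withdrawal | Handled by a destruction pathway (8) | Retained under 21 CFR 812.140 (9.6, 9.7) |
| Adverse events in a withdrawn patient | No exception from that pathway (8) | All AEs documented (9.2); all SAEs recorded (9.3) |
| Place in the analysis | Randomized but unevaluable (4.1) | No analysis set or partial-data rule (6.1, 6.2) |

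No section states which rule takes precedence.

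**The case against.** The strongest objection is textual. The destruction sentence follows a condition about the patient withdrawing. The reasons for being withdrawn come afterwards, in a separate paragraph. Applying destruction to physician-initiated withdrawal is therefore a reading, not a statement. This stands, and the point is worded accordingly. But voluntary withdrawal sits in the same list and no other data rule is given, so a site could follow either reading. The sentence may also have been meant only for identifiable information, since section 11.5 describes coded data. As written, however, it covers the collected data. What the consent form says about data already collected cannot be checked from the documents reviewed.

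A reader might infer that the worst cases vanish from the safety record. The documents do not support that. Section 9 puts non-related events on the anesthesia record, section 11.2 requires source documentation, and sections 9.2, 9.3, 9.6 and 9.7 require documentation, UADE reporting and retention. The finding is an unresolved contradiction, not a demonstrated loss.

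A reader might also infer that one lost patient could shift the result by the full half-width, because 19.5 excess minutes/50 = 0.39. That holds the half-width fixed while adding a value 19.5 SD out. With 49 others at SD 1 minute, that arm's variance is (48 + 19.5² × 49/50)/49 = 8.58 (SD 2.9). The half-width becomes 1.96 × √((8.58 + 1)/50) = 0.86, so the shift is less than half of it.

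Finally, nothing in the documents shows that withdrawals will mostly reflect airway failure, or that the difference would reverse in sign.

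**Conclusion.** The concern holds as a defect in a stated rule. Section 8, read with section 4.1, permits irreversible and outcome-related removal of primary-endpoint data, and it contradicts the safety-documentation and retention sections without saying which governs.

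If withdrawals stay at or below 1%, the expected bias is small: about 0.04 to 0.07 SD for the single worst of 60 in one arm. It approaches the planned 0.39 SD only if many losses fall on the worst cases of one arm (0.29 to 0.36 SD for ten). These sizes rest on assumed ToLDE distributions and on worst-case selection. Section 4.1 itself says that existing data are lacking.

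The case for changing the text rests on irreversibility and on the conflict between sections, not on a large expected bias.

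**What to change.** Replace the destruction sentence in section 8 with a rule to this effect:

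- Data collected up to withdrawal are retained and analysed in the assigned group.
- AE, SAE and UADE records are never destroyed.
- If the patient withdraws consent, no new study data are collected. Data already obtained are kept, as the consent form states.
- If the investigator withdraws the patient, SpO2, airway-support and AE data continue to be recorded through the 60-minute window, whatever the clinical decision.

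Reconcile section 8 with sections 4.1, 9.2, 9.3, 9.6 and 9.7, so that a withdrawn patient with usable data is not automatically unevaluable. Section 10.2 ("The data collection will be terminated if an identifiable adverse event happens") must be aligned as well, or continued recording after an adverse event would still be barred. Say in section 6.2 how an incomplete ToLDE window is handled, and report withdrawals by arm and reason.

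The cost is a short amendment and matching consent wording, including telling patients that data collected before withdrawal are kept. No extra patients or procedures are needed.
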